8.2.4. Safety Measures

Safety will be assessed using:

- Incidence of treatment-related adverse events (TEAEs)
- Incidence and severity of treatment-emergent adverse events (TEAEs)
- Incidence of serious adverse events (SAEs)
- Incidence of TEAEs and SAEs leading to discontinuation of study medication.
- Changes in blood chemistry, hematology and coagulation parameter results
- Changes in vital signs including temperature, pulse, respiratory rate, systolic and diastolic blood pressure
- Changes in physical examination results
- Changes in electrocardiogram (ECG) results

8.3. SAMPLE SIZE DETERMINATION AND RATIONALE

This is a randomized study with two treatment groups. The subjects will be randomized to the treatment groups (leronlimab or placebo) in a 2:1 ratio.

A total of three hundred ninty (390) subjects will be randomized in a 2:1 ratio to leronlimab or placebo groups with the goal of having 369 subjects (246 subjects in the leronlimab and 123 in the placebo group) complete the study.

The sample size is obtained based on the assumption that there will be a clinically meaningful difference in the rate of Day 28 mortality (i.e., 15% which is 45% Day 28 mortality rate for the placebo group versus 30% Day 28 mortality rate in the leronlimab group). This sample size is based on using a 2-sided Z-tset test with 80% power and an overall significance level of 0.05. The expected dropout rate is 5%. To accommodate subject attritions due to the potential discontinuations, it is recommended randomizing an estimated 390 subjects (260 in the leronlimab group and 130 placebo group). Sample size is estimated using PASS sample size software, tests for two proportions.

CONFIDENTIAL Page 78 of 108

A single arm, non-randomized, open-label phase is added to the protocol after completion of enrollment in the Randomized Phase of the study in order to provide access to leronlimab for the eligible patients. Approximately, 100 subjects are expected to be enrolled in the non-randomized phase. Enrollment will remain open until the decision is made by Sponsor and/or FDA to close the recruitment. No statistical power calculation is used for the sample size calculation for the non-randomized portion of the trial.

8.4. RANDOMIZATION

This is a multi-center randomized clinical trial. The randomization will use block size of 3 with a 2:1 ratio of leronlimab group and placebo group to ensure balanced distribution of leronlimab group and placebo subjects. An individual, independent of the clinical trial team, will develop the randomization schedules. The actual randomization assignment will be made through an Interactive Web Based Response System (IWRS) called WebView[®]. Subjects who have provided written informed consent and have met all the inclusion criteria and none of the exclusion criteria will be randomized to one of the treatment groups.

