7.21. RANDOMIZATION

Subjects who are eligible to participate in the trial will be randomized to one of the treatment groups via IWRS (Interactive Web Based Randomization System) at Visit 2 prior to IP administration. The randomization will be central with a 2:1 ratio of Active Treatment to Control Treatment to ensure even distribution of Active and Control subjects.

CONFIDENTIAL Page 75 of 108

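### Protocol 8.4 and SAP 2.4 print a single block size of 3 at 2:1, so the size is not concealed; the realistic gain in predictability is small, and varying, undisclosed sizes would reduce it cheaply for allocations still to be made.

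*Protocol*

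**What the plan says.** Protocol 8.4 (Randomization): "The randomization will use block size of 3 with a 2:1 ratio of leronlimab group and placebo group". SAP 2.4 carries the same sentence. The stated purpose is balance between the arms. No other size is given, and nothing is said about varying the size or withholding it from sites.

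Protocol 7.21 adds: "The randomization will be central with a 2:1 ratio of Active Treatment to Control Treatment". Protocol 8.5 stratifies by clinical status (three levels), by prior off-label immunomodulator use and, if sites are multinational, by region. Site is not a stratification factor. Protocol 3.1 allows up to 30 centers.

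Protocol 8.6 blinds subjects, investigators and the sponsor and CRO staff who manage the study. It excepts an unblinded pharmacist or designated site staff, who prepare the syringes (6.1.3). Placebo is 0.9% saline (6.1), whereas the active solution may be opalescent or yellow (6.1.2). Protocol 8.6 also refers to a separate Randomization Plan, which is not among the documents.

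**The concern.** Three is the smallest block that can hold a 2:1 ratio. When it is the only size, anyone who learns or guesses that one subject in a block received placebo knows that all later subjects in that block receive leronlimab. Anyone who knows of two leronlimab subjects knows that the third receives placebo. Concealing the size would weaken these deductions, but the size is printed in the investigators' working document.

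Two things are at stake. If the next assignment can be foreseen, the decision to enrol a particular patient may depend on it, and that can bias even an objective endpoint such as Day 28 mortality. Also, one unmasked subject can unmask others. That matters more for the secondary endpoints that depend on discharge and activity limitation, where judgement enters.

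The documents show ways in which a single assignment could become known: unblinded staff at the site, emergency unblinding with written notice to the investigator (Protocol 8.7.2), and a possible difference in appearance between saline and the active solution.

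**Working it through.** **Inputs.** Block size 3 at 2:1 (Protocol 8.4, SAP 2.4). Protocol 8.3 gives the ratio, "The subjects will be randomized to the treatment groups (leronlimab or placebo) in a 2:1 ratio", and the numbers: "it is recommended randomizing an estimated 390 subjects (260 in the leronlimab group and 130 placebo group") and "369 subjects (246 subjects in the leronlimab and 123 in the placebo group) complete the study".

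**The plan's own figures.** With "45% Day 28 mortality rate for the placebo group versus 30% Day 28 mortality rate in the leronlimab group", two-sided 0.05 and 80% power, the unpooled two-proportion formula gives, for placebo, (0.45×0.55 + 0.30×0.70/2) × (1.960 + 0.842)² / 0.15² = 0.3525 × 7.849 / 0.0225 ≈ 123. That means 246 on leronlimab and 369 in total, as stated. For 5% dropout, 369/0.95 = 388.4, rounded up to 389 and then to 390. In blocks of 3, 390/3 = 130 blocks, which gives 260 and 130. These figures reproduce. The documents state no predictability figure.

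**Ceiling: all earlier allocations known.** The three equally likely orders (P = placebo, A = leronlimab) have these positions that are certain from the earlier ones:

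| Order | Certain positions |
|---|---|
| PAA | 2 |
| APA | 1 |
| AAP | 1 |

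The expected share is (2 + 1 + 1)/9 = 4/9 = 44.4%, or 390 × 4/9 ≈ 173 allocations. Within one block the share is 1/3 or 2/3. Placebo is certain in advance only in AAP, that is, for one third of placebo subjects. Best-guess accuracy is (2/3 + 2/3 + 1)/3 = 77.8%, against 66.7% from always guessing leronlimab.

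**Partial knowledge.** Suppose the observer knows each earlier allocation with probability q and also knows where blocks start.
- Position 1 is never certain.
- Position 2 is certain if position 1 was placebo and was seen: q/3.
- Position 3 is certain if the placebo came earlier and was seen (2q/3), or if both earlier subjects were on leronlimab and both were seen (q²/3).

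The mean over the three positions is (q/3 + 2q/3 + q²/3)/3 = q/3 + q²/9.

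| q (assumed) | Certain share |
|---|---|
| 1 | 0.333 + 0.111 = 44.4% |
| 0.5 | 0.167 + 0.028 = 19.4% |
| 0.25 | 0.083 + 0.007 = 9.0% |
| 0.1 | 0.033 + 0.001 = 3.4% |
| 1/30 | 0.0111 + 0.0001 = 1.1% |

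The last row corresponds to one of 30 equal sites whose own subjects are all unmasked.

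**Alternatives, full knowledge.** Exact enumeration gives 13/45 = 28.9% for fixed blocks of 6 and 3/14 = 21.4% for fixed blocks of 9. Simulation of randomly mixed sizes, where the observer knows which sizes are possible but not which is in use, gives about 10% for 3 and 6, 5% for 6 and 9, and 4% for 3, 6 and 9.

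**The case against.** The strongest reply is that 44% describes an observer who does not exist in this trial. Allocation is central and shared across up to 30 centers, site is not a stratum, and those who enrol are blinded. Unblinded pharmacy staff already know their own subjects' arms whatever the block size; the block adds only predictions about others, who are often at other sites. Mortality is objective. Small blocks also protect the 2:1 ratio in sparse strata, and Protocol 8.5 creates at least 3 × 2 = 6 strata before region. All of this stands, and it is why the working gives a range and not only the ceiling. What remains is a site that supplies most of a small stratum, where q could be well above 1/30. The documents give no recruitment by site or stratum, so this can be neither confirmed nor excluded.

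A second reply is that the change comes too late. The protocol dated 28-Dec-2020 adds the open-label phase once randomized enrolment is complete, and that phase has no randomization. On the natural reading, the planned 390 have been allocated. This also stands: rewriting SAP 2.4 outright could describe a schedule that was not used. SAP 5.2.6 does provide for added subjects, with a stated maximum of 1170, but the documents do not say whether any were added.

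Finally, that the size is fixed is an inference. It is a fair one, since both documents print only one size, but the Randomization Plan has not been seen.

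**Conclusion.** The point holds as a weakness in concealment, of low to moderate severity. The plan uses the most predictable block available at 2:1 and prints its size where sites can read it. The share of allocations that could be deduced with certainty is at most 44.4% in expectation and falls to between about 1% and 19% for q between 1/30 and 0.5. These figures assume complete blocks, known block starts and assumed values of q; incomplete final blocks change them slightly.

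A reader might infer that nearly half of the allocations were predictable in practice, or that the randomization was compromised. The documents support neither reading. The first needs sight of every consecutive allocation in a stratum, which no blinded enrolling role is given. For the second, nothing in the documents shows that any assignment was predicted or that any enrolment was selective.

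**What to change.** For every randomized allocation not yet made, including any added under SAP 5.2.6:
- Use randomly permuted blocks of varying size, all multiples of 3 at 2:1 (for example 3, 6 and 9), within the existing strata.
- In Protocol 8.4, replace the block size with a statement that randomly permuted blocks of varying size are used.
- Record the sizes only in the Randomization Plan, with restricted access.

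For allocations already made in blocks of 3, keep that size in SAP 2.4 as the factual description, say to which allocations it applies, and report the fixed, disclosed size as a limitation in the clinical study report. If no randomized allocations remain, this last step is the whole of the change.

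The cost is a revised schedule, a few sentences and slightly more imbalance in small strata. At any moment the placebo count in a stratum can differ from one third of its subjects by at most 2/3 of a subject with blocks of 3 (one placebo first: 1 − 1/3), 4/3 with blocks of 6 (2 − 2/3) and 2 with blocks of 9 (3 − 1). Against 390 subjects this is minor.

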8.5. STRATIFICATION

Randomization will be stratified into one of the three categories based on clinical status of the study at baseline:

- Hospitalized, not in intensive care unit (ICU)
- Hospitalized, in ICU, on mechanical ventilation, not on vasopressors
- Hospitalized, in ICU, on mechanical ventilation, on vasopressors

For the purpose of stratification, on vasoporessors dose is defined as: norepinephrine $>20\mu g/min$ and/or vasopressin >0.04 units/kg/min.

Subjects will also be stratified for the prior use of off-label immunomodulatory treatments for COVID-19.

Additionally, randomization will be stratified by region (North America, Europe etc.) if multinational sites are involved in the study.

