3.3.1. Inclusion Criteria

Potential subjects are required to meet all of the following criteria for enrollment into the study:

- 1. Male or female adult \geq 18 years of age at time of screening.
- 2. Subjects hospitalized with severe or critical illness caused by coronavirus 2019 infection as defined below:

Severe Illness:

• Diagnosed with COVID-19 by standard RT-PCR assay or equivalent testing within 5 days of screening

AND

- Symptoms of severe systemic illness/infection with COVID-19:
 - o At least 1 of the following: fever, cough, sore throat, malaise, headache, muscle pain, shortness of breath at rest or with exertion, confusion, or symptoms of severe lower respiratory symptoms including dyspnea at rest or respiratory distress

AND

- Clinical signs indicative of severe systemic illness/infection with COVID-19, with at least 1 of the following:
 - o RR \geq 30, HR \geq 125, SaO2 <93% on room air or requires \geq 2L oxygen by NC in order maintain SaO2 ≥93%, PaO2/FiO2 <300

AND

- No criteria for Critical Illness:
 - o None of the following: Respiratory failure (defined by endotracheal intubation and mechanical ventilation, oxygen delivered by high-flow nasal cannula, noninvasive positive pressure ventilation, or clinical diagnosis of respiratory failure in setting of resource limitations), Septic shock (defined by SBP < 90 mm Hg, or Diastolic BP < 60 mm Hg), Multiple organ dysfunction/failure

CONFIDENTIAL Page 45 of 108

Critical Illness:

 Diagnosed with COVID-19 by standard RT-PCR assay or equivalent testing within 5 days of screening

AND

- Evidence of critical illness, defined by at least 1 of the following:
 - Respiratory failure defined based on resource utilization requiring at least 1 of the following:

Endotracheal intubation and mechanical ventilation, oxygen delivered by high-flow nasal cannula, noninvasive positive pressure ventilation, ECMO, or clinical diagnosis of respiratory failure (in setting of resource limitation)

OR

• Shock (defined by SBP < 90 mm Hg, or Diastolic BP < 60 mm Hg or requiring vasopressors)

[figure not shown]
OR

- Multiple organ dysfunction/failure
- 3. Subject, if intubated, positive end-expiratory pressure (PEEP) <15 cmH2O with PaO2/FiO2 >150 mmHg.
- 4. Electrocardiogram (ECG) with no clinically significant findings as assessed by the Investigator.

Note: Below are the examples of clinically significant and non-clinically significant ECG abnormalities:

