3.3.2. Exclusion Criteria

Potential subjects meeting any of the following criteria will be excluded from enrollment:

- 1. Subjects with do-not-resuscitate (DNR) and/or do-not-intubate (DNI) orders or expected to be made DNR/DNI in setting of resource limitations or family wishes.
- 2. Not a candidate for dialysis or continuation of care (or full medical support) in setting of resource limitations.
- 3. Subject on continuous vasopressors (at the dose of norepinephrine >20µg/min and/or vasopressin >0.04 units/kg/min) for >48 hours at time of screening.
- 4. Subjects who have a history of allergic reactions attributed to compounds of similar chemical or biologic composition to leronlimab (PRO 140) are not eligible.
- 5. Inability to provide informed consent or to comply with test requirements
- 6. Consideration by the investigator, for safety reasons, that the subject is an unsuitable candidate to receive study treatment
- 7. Pregnancy or breast feeding
- 8. Subject participating in another study with for an investigational treatment for COVID-19.

Note: Subject who were prescribed (1) hydroxychloroguine or chloroguine with or without azithromycin, (2) Remdesivir, (3) convalescent plasma therapy, or (4) immunomodulatory treatments (including but not limited to sarilumab, clazakizumab, tocilizumab, and anakinra) for the off-label treatment of COVID-19 prior to study enrollment may be included and may continue to receive these agents as part of standard-of-care.

CONFIDENTIAL Page 47 of 108

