#### 2.5 STRATIFICATION

Randomization will be stratified into one of the three categories based on clinical status of the patient at baseline:

- Hospitalized, not in intensive care unit (ICU)
- Hospitalized, in ICU, on mechanical ventilation, not on vasopressors
- Hospitalized, in ICU, on mechanical ventilation, on vasopressors

For the purpose of stratification, on vasoporessors dose is defined as: norepinephrine  $>20\mu g/min$  and/or vasopressin>0.04 units/kg/min.

Subjects will also be stratified for the prior use of off-label immunomodulatory treatments for COVID-19.

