# 9.2.1 Primary Efficacy Endpoint

The primary endpoint for the study is all-cause mortality at Day 28. All-cause mortality at Day 28 will be summarized. The estimated difference in mortality rates along with 95% confidence interval and p-value will be calculated using Logistic Regression adjusting for stratification factors (Ge et al. 2011).

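### The 'on vasopressors' stratum uses exclusion 3's dose threshold, so ventilated ICU subjects on vasopressors at or below that dose are grouped with those on none

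*Protocol*

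**What the plan says.** **Stratification.** Protocol 8.5 and SAP 2.5 set three clinical-status levels at baseline: not in ICU; in ICU, ventilated, not on vasopressors; and in ICU, ventilated, on vasopressors. Both documents then narrow the last label. The protocol writes "For the purpose of stratification, on vasoporessors dose is defined as" and the SAP "For the purpose of stratification, on vasoporessors dose is defined as: norepinephrine", each followed by norepinephrine above 20 µg/min and/or vasopressin above 0.04 units/kg/min.

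**Exclusion 3 (Protocol 3.3.2).** "Subject on continuous vasopressors (at the dose of norepinephrine" above 20 µg/min and/or "vasopressin >0.04 units/kg/min) for >48 hours at time of screening". The drugs, figures and units are the same as in the stratum definition.

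**Critical illness (Protocol 3.3.1).** One qualifying route is "Shock (defined by SBP < 90 mm Hg, or Diastolic BP < 60 mm Hg or requiring vasopressors", with no minimum dose.

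**Primary analysis (SAP 9.2.1).** The mortality difference, its interval and the p-value "will be calculated using Logistic Regression adjusting for stratification factors". No other baseline covariate is named. SAP 8.3 also puts the stratification factor into each imputation model.

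**The concern.** The label and the content of the stratum differ. A reader of the strata would expect the second and third levels to separate ventilated subjects with and without vasopressor support. They separate subjects above a specific dose from everyone else who is ventilated in ICU, including those on a vasopressor at or below that dose. The inclusion criteria take the opposite view, since any vasopressor requirement there counts as shock.

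Vasopressor use at baseline plausibly predicts Day 28 death. Where the factor does not capture it, the randomisation does not balance it and the primary model does not adjust for it. Protocol 8.9.2 leaves important prognostic factors to the SAP, and SAP 9.2.1 adds none beyond the strata. At stake are precision and protection against chance imbalance in the primary comparison, together with an imputation model that carries the same coarse factor.

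**Working it through.** **1. The plan's own sample size.** With 45% against 30% mortality, two-sided 0.05, 80% power, 2:1 allocation and unpooled variance:

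placebo n = (1.96 + 0.8416)² × (0.45×0.55 + 0.30×0.70/2) / 0.15² = 7.849 × 0.3525 / 0.0225 ≈ 123, so 369 in total.

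This matches the stated 369. Dividing by 0.95 gives 389, against 390 stated. The calculation uses no stratum information, so nothing below changes it.

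**2. The three definitions side by side.**

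| Place | Norepinephrine | Vasopressin | Duration | Judged at |
|---|---|---|---|---|
| Stratum (Protocol 8.5, SAP 2.5) | >20 µg/min | >0.04 units/kg/min | none | baseline |
| Exclusion 3 | >20 µg/min | >0.04 units/kg/min | continuous, >48 h | screening |
| Shock criterion | any requirement | any requirement | none | eligibility |

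At screening, a subject above the dose is eligible only with no more than 48 hours of continuous use. A ventilated ICU subject at or below the dose meets the shock criterion and is coded as not on vasopressors.

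**3. Timing.** V2 may fall up to 7 days after screening. A subject at exactly 48 hours at screening could have 48 + 7×24 = 216 hours by V2 and still be eligible. A subject may also first pass the dose after screening.

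**4. Scale, from the protocol's SOFA table (Appendix 17.3).** Norepinephrine above 0.1 mcg/kg/min scores +4, the highest cardiovascular score. Body weight is an assumption:

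- 50 kg: 0.1 × 50 = 5 µg/min
- 70 kg: 0.1 × 70 = 7 µg/min
- 120 kg: 0.1 × 120 = 12 µg/min

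A ventilated 70 kg subject on more than 7 and up to 20 µg/min, with no vasopressin above its threshold, has the top SOFA cardiovascular score and is coded as not on vasopressors. This shows that the mixed group can include severe cases. It does not show how many.

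**5. Size of the loss, illustration only.** The documents give no stratum sizes and no vasopressor prevalence. Assume:

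- 30% of subjects are in the ventilated, not-on-vasopressors level.
- Half of them are on a lower-dose vasopressor, with 60% mortality.
- The other half have 50% mortality (case A) or 40% (case B).
- Overall mortality is (2×0.30 + 0.45)/3 = 0.35, from the plan's own rates.
- The remaining 70% are treated as one group.

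Variance added by the covariate inside the level = 0.30 × 0.5 × 0.5 × d²:

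- A: 0.075 × 0.10² = 0.00075
- B: 0.075 × 0.20² = 0.00300

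Variance left after the strata = 0.35×0.65 − 0.30×0.70×(level mortality − rest mortality)²:

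- A: level 0.55, rest (0.35 − 0.165)/0.70 = 0.264; 0.2275 − 0.0171 = 0.2104
- B: level 0.50, rest (0.35 − 0.150)/0.70 = 0.286; 0.2275 − 0.0096 = 0.2179

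Incremental R² = 0.00075/0.2104 = 0.0036 (A) and 0.0030/0.2179 = 0.0138 (B).

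Equivalent subjects = 390 × [1/(1 − R²) − 1], about 1 (A) and 5 (B).

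**The case against.** The strongest reply is that this is a design choice. The threshold is explicit and the same in both documents, and sites can apply it. Stratifying on high-dose support is a legitimate prognostic choice, and a sparse level would not invalidate the analysis. All of that stands. Control is also partial rather than absent, because ICU and ventilation status and high-dose use are stratified and adjusted for.

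Three stronger readings are tempting, and the documents do not support them.

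- **The stratum can hold only subjects within 48 hours above the dose.** Exclusion 3 is assessed on continuous use "for >48 hours at time of screening", while the stratum is assigned at baseline, so longer exposure at randomisation is possible.
- **Every other vasopressor-treated subject is coded as not on vasopressors.** This holds only for ventilated ICU subjects. Non-ICU subjects fall in the first level whatever their vasopressor use. ICU subjects who are not ventilated fit none of the three levels, which is a separate gap.
- **The high-dose level will be very small.** It may be sparse, but no counts are given.

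It is also fair to say that an any-dose covariate does not capture the whole shock definition, because a hypotensive subject on no vasopressor would still be coded no. The covariate repairs the vasopressor part only.

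**Conclusion.** The point holds as a minor weakness. One threshold serves both exclusion 3 and the stratum, and it conflicts with the shock criterion. The consequence is that ventilated ICU subjects on vasopressors at or below that dose share a level with those on none. The primary model then controls only partly for baseline vasopressor use.

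The cost is some precision and possible chance imbalance. A reader might infer bias or an inflated type I error, but neither follows: chance imbalance in a randomised comparison is not bias, and the test remains valid without the extra covariate.

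The gain from adding the covariate is probably small and cannot be computed from the documents. The 1 to 5 subjects rest wholly on the assumed split and mortality rates. A reader might reach a much larger gain by comparing lower-dose vasopressor subjects with all other subjects. That comparison includes the non-ICU patients and credits the new covariate with variance that the ICU and ventilation levels already explain.

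**What to change.** **SAP 9.2.1, before unblinding:** add baseline vasopressor use at any dose (yes/no) as a covariate beside the stratification factors, taking the last value before randomisation as in SAP 8.1. The schedule of assessments lists vasopressor use at V1 and V2, so no new data are needed. Protocol 7.20 omits V2 from its list of visits, but the schedule and Protocol 4.2.1 include it. The cost is one sentence and one model term.

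**Protocol 8.5 and SAP 2.5:** reconcile the stratum definition with the shock criterion and with exclusion 3, or state why the stratum is meant to capture high-dose support only. No dose is proposed here. Changing the strata themselves would do little now: the open-label phase follows completion of randomised enrolment, so a new definition would matter only if a sample-size increase under SAP 5.2.6 reopened randomisation. The covariate is the part that can be acted on.
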